## 9.2 TABLE 4: RESTASIS STUDY VISIT SCHEDULE

Restasis								Restasis CROSSOVER to TearCare					
Visit	Baseline	Day 0	Day 1	Wk 1	1 M	3 M	6 M/TearCare	Post Procedure			9 M	12 M	
Window days	-7 to 0	0	1	5-9	21-35	70-90	150-180	Day 1	Wk 1	1 M	220-280	320-390	
								1	5-9	21-35			
Informed Consent a	X												
Demographics, Ocular & Medical Hx	X												
Medication use	X			X	X	X	X		X	X	X	X	
Questionnaires (OSDI, SANDE, Eye Dryness Score)	X			X	X	X	X		X	X	X	X	
BCVA b	X		X c	X c	X	X	X	X c	X c	X	X	X	
Blink rate	X			X			X		X			X	
Slit Lamp Exam	X		X	X	X	X	X	X	X	X	X	X	
TBUT	X			X	X	X	X		X	X	X	X	
Corneal Staining	X			X	X	X	X		X	X	X	X	
Conjunctival Staining	X			X	X	X	X		X	X	X	X	
Schirmer Test	X			X	X		X		X	X		X	
MGSS	X			X	X	X	X		X	X	X	X	
IOP d	X		X	X	X	X	X	X	X	X	X	X	
Subject Eligibility	X												
Randomization	X												
Restasis (1gtt BID)		X	X	X	X	X							
AE Assessment	X	X	X	X	X	X	X	X	X	X	X	X	
Crossover and TearCare Procedure							X						
Treatment preference questionnaire												X	
Eye Lubricant/Drop Log					X	X	X		X	X	X	X	

a Subjects may sign the informed consent up to 60 days in advance of the baseline visit.

b Restasis must be dispensed within 7 calendar days of the Baseline visit. If scheduling permits, it may be dispensed on the same day as the Baseline visit following Randomization.

c BCVA should be collected after manifest refraction using ETDRS visual acuity chart

d On Day 1 and Week 1, Best Corrected Spectacle Visual Acuity (BCSVA using ETDRS) is measured without manifest refraction (MR). If the VA has worsened by  $\geq 10$  letters (per ETDRS) from baseline, then MR should be performed, the ETDRS measurement should be repeated, and the VA post-MR should be recorded.

e IOP measured via applanation tonometry should be measured at baseline using standard of practice at each site with the same method to be used for all consecutive visits in the study.

### **9.3 NUMBER OF SUBJECTS, DURATION OF FOLLOW-UP AND STUDY DURATION**

A sample size of 200 subjects is estimated to provide sufficient power (90%) for this study. Nonetheless, given the 24 months follow up period, and in an attempt to collect additional data regarding changes in the signs and symptoms of dry eye disease, a total of up to 350 subjects will be enrolled and randomized in the study. Assuming a 15% screen failure rate, approximately 412 subjects will be enrolled to obtain up to 175 randomized subjects in each study group. All subjects will be followed for up to 24 months.

It is anticipated that enrollment in the study will take 16-26 months. Including the 24 months follow-up period, the study is expected to last 40-50 months.

### **9.4 MATERIAL AND EQUIPMENT**

A listing of general equipment and materials required at the investigational site for the study is provided below.

- a. TearCare SmartHub Kit (includes a SmartHub, charging nest and charging adapter)
- b. TearCare SmartLid Devices and Clearance Assistant Plus Devices
- c. TearCare wipes
- d. Restasis (Cyclosporine 0.05%) Ophthalmic Emulsion
- e. ETDRS Visual Acuity System
- f. Slit lamp
- g. Wratten filter (yellow) (for corneal staining)
- h. Goldmann Tonometer or other applanation tonometer
- i. Meibomian Gland Evaluator (TearScience, Inc.)
- j. Fluorescein sodium strips (for TBUT and corneal staining)
- k. Lissamine green strips (for conjunctival staining)
- l. Filter strips (for the Schirmer test)
- m. Preservative-free sterile saline
- n. Proparacaine 0.5% or tetracaine 0.5% ophthalmic drops
- o. Akten® (lidocaine hydrochloride ophthalmic gel) 3.5% or equivalent
- p. Stopwatch
- q. Ruler
- r. Sterile scissors
- s. Thermometer
- t. Webcam and/or laptop

## **9.5 INFORMED CONSENT AND POINT OF ENROLLMENT**

The IRB-approved informed consent will be presented and explained to each prospective subject by the investigator or a trained clinical professional. Once the subject has had ample time to read the consent form, has been informed of all aspects of the study, and has had an opportunity to ask questions, the subject will be given a choice to voluntarily confirm his or her participation in the study as documented by completion of the Informed Consent. After signing the Informed Consent and the HIPAA (Health Insurance Portability and Accountability Act) authorization, the subject can then proceed with the baseline visit. The baseline visit should be performed within 60 days of the subject signing the informed consent. The subject has the right to withdraw from the study at any time without consequences, as indicated in the Informed Consent Document.

The subject's signed and dated informed consent must be obtained before conducting any procedure specifically for the study. Subjects are enrolled upon signing the ICD even if they subsequently fail to meet the eligibility criteria.

The principal investigator(s) must retain the original, signed written Informed Consent Document. A copy of the written Informed Consent Document must be given to the subject.

## **9.6 BASELINE AND STUDY GROUP VISIT(S)**

### **9.6.1 SCHEDULING THE BASELINE AND DAY 0 VISIT(S)**

To facilitate scheduling, the Baseline and Day 0 Visits may be performed on the same day or on two separate days and following randomization. If these visits are performed over two days, Day 0 must be within 7 calendar days of the Baseline Visit.

Refer to Table 3 for which tests and exams are to be performed at each visit for both groups. Endpoint assessments performed during the Baseline visit must be performed by a Masked Assessor (See Section 9.9).

Since dry eye drops and lubricants can affect the endpoint assessments, instruct subjects not to use any of these products within 2 hours of the Baseline visit.

### **9.6.2 BASELINE EXAMS, TESTS AND QUESTIONNAIRES**

After the subject has signed the informed consent form and agreed to participate in the study, the exams, tests, and questionnaires listed in the Baseline column of Table 3 should be performed. Refer to Appendix A for instructions for performing the exams and administering the questionnaires.

At this visit, subjects should undergo the following tests and exams, performed in the order indicated below, to screen them for the study qualification and to record baseline data. Items with an asterisk (\*) must be performed by a Masked Assessor (Refer to Section 9.9 for more information on the Masked Assessor).

1. Questionnaires: OSDI, SANDE and Eye Dryness VAS
2. Demographics, medical and ocular history
3. Medication use: ocular and systemic
4. Manifest refraction and ETDRS Best-corrected visual acuity\*
5. Blink Rate\*
6. Slit Lamp Exam\*
7. Tear Breakup Time\*
8. Corneal Staining\*
9. Conjunctival Staining\*
10. Schirmer Test\*
11. Meibomian Gland Secretion Scoring\*
12. Intraocular pressure\*
13. Adverse Event Assessment

If, at any point during the visit the subjects fails to meet a subject selection criterion, then the visit can be terminated. Subjects who fail to meet all the selection criteria will be considered a screen failure and will be withdrawn from the study.

Subjects who fail screening may be re-screened for the study after 30 days. If they are re-enrolled, they should be assigned a new subject ID.

NOTE: Questionnaires and exam data collected on subjects prior to enrollment as part of the routine clinical practice may be used to pre-screen for the study. However, once the subject signs the consent form and is enrolled in the study, these questionnaires and exams must be repeated following the protocol procedures.

After all required measurements have been obtained and it has been confirmed that the subject meets all the Subject Selection Criteria, then the subject will be Randomized.

### **9.6.3 RANDOMIZATION**

Subjects will be randomized to either the TearCare (i.e., “device group”) or Restasis (i.e., “control group”). Randomization will be performed using a 1:1 ratio and will be stratified by site. Computer-generated randomization will be administered through the electronic data capture (EDC) system.

Following randomization, the subject should undergo the applicable procedures described in the sections below.

---

#### 9.6.4 PROCEDURE FOR TEARCARE (STUDY DEVICE GROUP)

Subjects randomized to the study device group (TearCare) will undergo the following procedure bilaterally. Refer to the TearCare Instructions for Use for detailed instructions for operating the TearCare System.

1. Obtain a new set of SmartLid devices and a TearCare SmartHub with enough battery left for at least one procedure.
2. Position the subject at the slit lamp to perform debridement of the eyelid margin followed by expression of the meibomian glands such that expression takes place within 3 minutes of completion of the thermal portion of the procedure.
3. Apply 1 drop of proparacaine or tetracaine into each eye.
4. Visualize the lid margin and line of Marx's (LOM) and debride eyelid margins by sweeping (very gently scraping) the debridement edge across the LOM back and forth going over meibomian gland orifices. Start nasally and work laterally multiple times using gentle pressure until the eyelid margins appear free of debris, keratin, and gland capping. Often the gland orifices become visible at this point.
5. Wipe the subject's eyelids and temple with the TearCare wipes to remove any make-up, oil, dirt, or lotion. Allow the skin to dry or pat dry with a tissue. Use care not to allow any of the wipe to get into the eye.
  - a. ***Caution: Eyelid cleansing may lead to skin irritation, which would put a patient at increased risk for thermal injury. If the patient is observed to have skin irritation, or if the patient complains of skin irritation after eyelid cleaning, do not proceed with the TearCare treatment.***
6. Remove the liner from the upper SmartLid to reveal adhesive. Continue to prebend the SmartLid, if needed. Peel from temporal tab towards nasal and discard the liner. (For each eye)
7. Place a pair of SmartLid devices on the subject's eyelids and affix the temple housing to the subject's temple. Use the clip to secure the cables behind the subject's head.
8. Connect the SmartLid devices to the SmartHub.
9. Inform the subject that the SmartLid devices will heat up very quickly once the TearCare procedure is started.
10. Start TearCare procedure. Subjects should be encouraged keep their eyes open and blink naturally during the TearCare procedure.
11. If the subject indicates the temperature is too hot, decrease the temperature set point to a setting that is comfortable for the subject.
12. Following the thermal portion of the TearCare procedure, remove the SmartLid devices from the subject, position the subject at the slit lamp biomicroscope, repeat debridement if deemed necessary and using the Clearance Assistant Plus Device, express the meibomian glands in all 4 eyelids using the following technique:
  - a. Think of each eyelid as having 3 zones: nasal, central & temporal.

- b. For each zone, start at the fornix and work your way up to the margin.
- c. Position the forceps horizontal, parallel to the margin.
- d. Apply moderate continuous pressure and adjust based on the gland output.
- e. Perform a second pass on the same eyelid to further express the glands.
- f. After treating the lower and upper eyelids, repeat expression on all 4 lids to ensure complete expression. Additional passes of expression may be performed to ensure complete expression.
- g. Should the subject experience discomfort, it is reasonable to apply additional topical anesthetic (i.e., proparacaine or tetracaine). Alternatively, Akten® (lidocaine hydrochloride ophthalmic gel) 3.5% or equivalent may be applied into the lower eyelid fornices.
- h. The goal is to express each zone until the meibum coming out is clear. Typically, complete expression takes approximately 5 minutes/eye.

#### **9.6.5 RESTASIS DISTRIBUTION (CONTROL GROUP)**

Subjects randomized to the control group (Restasis) will be provided with Restasis® (Cyclosporine 0.05% ophthalmic emulsion) for use in both eyes. Subjects should be instructed to follow steps below while administering Restasis:

Preparing the bottle for first-time use:

- a. Pull off shipping cover by pulling straight up. Remove the pull tab on the olive green colored protective cap by pulling the end of the pull tab away from the bottle then winding it counterclockwise.
- b. Remove the olive green colored protective cap by pulling it straight up. Keep the colored protective cap. Prime the bottle for first time use by squeezing 2 drops onto a tissue. Do not let the bottle tip touch the tissue.
- c. After use, recap the bottle with the olive green colored protective cap by pushing straight down onto the bottle.
- d. Turn the bottle upside down a few times before putting drops in eyes to make sure the medicine is mixed well.
- e. Instill one drop in both eyes approximately 12 hours apart from each other. The first drop should be instilled between 7 to 8 AM and second drop between 7 to 8 PM.
- f. Do not discontinue use of medication unless instructed by the site staff.

The site staff should give intermittent calls to the subjects to check if they have enough supply of the drops that last until their next visit. Please instruct subjects to inform the site staff before they run out of the medication. Each subject will receive the first bottle on Day 0 (treatment day). All additional bottles of Restasis will be provided at the protocol defined follow-up visits (Week 1, Month 1, and Month 3). To avoid shortage of medication, please try to bring the subject in at the early part of the visit window. If this requires scheduling an additional visit in between the protocol defined visits, it will be

---

considered an unscheduled visit.

The subjects should be instructed to:

- a. Store Restasis® between 15-25 °C (59-77 °F)
- b. For contact lens wearers, drops should be instilled at least 15 minutes after the removal of the contact lenses.
- c. Restasis® can be used with lubricant eye drops, but you should wait at least 15 minutes between using each product. The lubricant eye drops/rescue drops used should be recorded on the Eye Lubricant/Drop log. Sites should make sure to review the log at each visit as described in Section 9.6.6.

#### **9.6.6 FOLLOW-UP INSTRUCTIONS FOR SUBJECTS**

Review the following instructions with subjects at the completion of the visit.

During study follow-up:

1. Dry Eye Lubricants/Tear Drops: Subjects should make every effort to refrain from using any dry eye drops or lubricants. If they require “rescue therapy” to relieve their symptoms, they should use the same type of tear drops or lubricants they were using prior to the study.
2. Dry Eye Lubricant/Tear Drop Log: Provide subjects with the Lubricant/Drop log and instruct them to record any use of drops or lubricants during the follow-up period.
3. Other Dry Eye Medications: Subjects should not use any other medications for dry eye disease (e.g., Doxycycline, Xiidra, etc.).
4. Other Treatments for Dry Eyes: Subject should not have any other treatments for dry eyes. For example, they should not use warm compresses or perform lid massage/scrub. They should not use the True Tear device or have any other in-office dry eye treatments. If the investigator feels the need for an alternative procedural intervention, administration of these treatments will result in the subject being excluded from the “Per Protocol” analysis from the time of initiation of these treatments forward.
5. Other Ocular Procedures: Subjects should be recommended not to opt for an elective ocular procedure such as cataract surgery, refractive surgery etc. unless medically warranted during the study duration. In case such a surgery/procedure is needed, the subjects should be exited from the study prior to the procedure unless the procedure is performed to treat an adverse event.
6. Antihistamines: Subjects should be advised not to use any antihistamines during the study duration. In case antihistamines are needed during the study duration, topical antihistamines should be tried prior to using oral antihistamines. In case oral or systemic antihistamines are required, subjects should be instructed to discontinue use of antihistamines at least 7 days prior to scheduled study visits. Subjects who are on preexisting stable dose of antihistamines prior to baseline should be instructed to discontinue use of antihistamines at least 7 days prior to scheduled study visits.

7. Use of Contact lens: Subjects should be advised not to use contact lenses at least 72 hours prior to the scheduled study visits.

## 9.7 FOLLOW-UP VISITS

### Prior to the Visit: Reminder Call

A few days before the follow-up visit, it is recommended that the coordinator contact the subject to remind them not to use dry eye drops or lubricants on the day of the follow-up visit since these products can affect the endpoint assessments. For the subjects assigned to Restasis group, subjects can use Restasis on day of follow up visits. Since Restasis drops can affect the endpoint assessments, instruct subjects not to use Restasis within 2 hours of the study visit.

### At the Beginning of the Follow-up Visit: Maintaining Masking of Study Personnel

Endpoint assessments performed during the Follow-up visit must be performed by the Masked Assessor (See Section 9.9).

At the beginning of the follow-up visit, the coordinator should remind the subject to not reveal their randomization group to the study personnel who will be performing the follow-up exams.

### Order of Procedures During the Follow-Up Visit

Follow-up procedures will be performed per the Study Schedule provided in Table 3 and Table 4 (pages 32, 33) and the methods included in Appendix A. Since certain tests/exams can impact the ability to perform other tests/exams, the following tests and exams should be performed in this order:

1. Questionnaires
2. Manifest refraction, if required per this protocol, and ETDRS Best-corrected visual acuity
3. Blink Rate
4. Slit Lamp Exam
5. Tear Breakup Time
6. Corneal staining
7. Conjunctival staining
8. Schirmer Test
9. Meibomian Gland Secretion Scoring
10. IOP
11. Assessment of adverse events

The following activities can be performed in any order:

- Medication Use
- Collection of Eye Lubricant/Drop Log (for all visits starting at 1 month)

## **9.8 PHOTOGRAPHY DURING EXAMS AND TEARCARE PROCEDURE**

Photographs or videos will be made during the baseline or follow-up exams or during the TearCare procedure. These images may be used for educational or training purposes. Subject consent must be obtained prior to taking any photographs or videos. Subjects do not have to agree to consent to being filmed in order to participate in the study.

## **9.9 MASKED ASSESSOR**

To reduce potential bias in the study, study staff performing endpoint assessments will be masked as to the subject's study group. In addition, to ensure consistency in performing the endpoint assessments the study staff member who performs the baseline assessments should also perform the follow-up assessments. An alternate Masked Assessor may be appointed to handle scheduling conflicts, but every effort should be made to have the same person performing all endpoint assessments throughout the study. Masked Assessors may not perform the randomization, the TearCare group procedure, or the distribution of Restasis medication to subjects randomized to the Restasis group.

The following assessments must be performed by a Masked Assessor:

- Manifest refraction and ETDRS Best-corrected visual acuity
- Blink Rate
- Slit Lamp Exam
- Tear Breakup Time
- Corneal Staining
- Conjunctival Staining
- Schirmer Test
- Meibomian Gland Secretion Scoring
- Intraocular pressure

## **9.10 MANAGEMENT OF DRY EYE SYMPTOMS DURING FOLLOW-UP**

During follow-up, subjects should refrain from using any non-study dry eye treatments, including drops, lubricants etc. If they require “rescue therapy” to relieve their symptoms, they should use the same type of tear drops or lubricants they were using prior to the study. They should document use of tear drops or lubricants on the Eye

**Lubricant/Tear Drop Log.**

Subjects should not use other medications for dry eye disease (e.g., Doxycycline, Xiidra, etc.) during the study. Use of these drugs will result in the subject being excluded from the “Per Protocol” analysis from the time of initiation of these drugs forward.

Subject should not be treated with other in office or at home dry eye treatments (e.g., IPL, TrueTear, iLux, punctal plugs, warm compresses, lid scrubs etc.) during the course of the study. Administration of these treatments will result in the subject being excluded from the “Per Protocol” analysis from the time of initiation of these treatments forward.

## **9.11 WITHDRAWAL AND DISCONTINUATION**

All subjects have the right to withdraw at any point during the study without prejudice. The investigator can discontinue any subject at any time if continued participation in the study would result in harm to the subject. All efforts should be made by the investigator to retain the subject in the study. If a subject withdraws prematurely from the study, a genuine effort must be made to determine the reason(s) the subject discontinued the study. The reason must be recorded in the subject’s file and on the Study Exit Form.

If a subject withdraws from the study post-randomization but prior to receiving the TearCare Procedure or Restasis®, then that subject may be replaced in the study by a newly enrolled subject.

## **9.12 SUBJECTS LOST TO FOLLOW-UP**

Subjects who do not show up for a follow-up must be contacted to attempt to have them come for the follow-up. For those subjects who cannot be reached, at least 3 phone call attempts should be made and documented. If a subject misses two consecutive follow-up visits without any contact with the study staff, the subject will be considered lost-to-follow-up unless there is further communication by the subject.

# **10 ADVERSE EVENTS (AES)**

Adverse Events are defined below. Adverse events that occur in the eye during the trial, whether considered to be device related or not, must be documented in the subject’s records. Non-ocular adverse events do not need to be recorded as adverse events unless they meet the definition of serious adverse event or are believed to be related to the study device or a study procedure. Date of the event, its severity, treatment (if any), and the assessed relationship of the event to the study device will be recorded on the Adverse Event Form. Conditions which exist at the time the subject is enrolled will be considered pre-existing conditions and do not need to be recorded as adverse events unless they increase in severity during the study.

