## 6.2 SAFETY ENDPOINTS

- **Primary Safety Endpoint**
  - Procedure (TearCare)/Treatment (Restasis)-related adverse events (all adverse events will be recorded)
- **Secondary Safety Endpoints**
  - Change in best corrected visual acuity (ETDRS)
  - Change in intraocular pressure (IOP)

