### 7.1 STUDY DEVICE AND CONTROL GROUP

In this study, TearCare procedures using the TearCare System (study device) will be compared with Restasis (control group).

TearCare procedures in this study will include an in-office eyelid debridement, 15-minute bilateral thermal session with the TearCare System, immediately followed by manual expression of the meibomian glands using the Clearance Assistant Plus device. Subjects randomized to TearCare will receive one in-office TearCare procedure within 7 days of the Baseline visit and at 5 Months. Beginning at 9 Months, subjects will receive an additional TearCare procedure when TBUT drops lower than Baseline or within 2 seconds of baseline AND if OSDI worsens by at least 15 points compared to the previous visit.

Subjects randomized to Restasis group will be required to self-administer 1 drop twice a day from baseline through the Month 6 visit. At Month 6, subjects will be crossed over to the TearCare group and will receive one (1) TearCare procedure.

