**10.1 DEFINITIONS OF AE, SAE, SADE, USADE**

Adverse Event	Any untoward medical occurrence in a subject who has been treated with the device that does not necessarily have causal relationship with the treatment.
Adverse Device Effect	Any unfavorable and unintended sign (including an abnormal laboratory finding), symptom, or disease that is possibly related to the study device.
Serious Adverse Event (SAE)	Any untoward medical occurrence that: 
 
• Results in death
 
• Is life-threatening
 
• Requires in-patient hospitalization or prolongs existing hospitalization
 
• Necessitates medical or surgical intervention to preclude permanent impairment of a body function or permanent damage to a body structure
 
• Sight threatening
 

Unanticipated Adverse Device Effect	Any serious adverse effect on health or safety, any life-threatening problem or death caused by, or associated with a device if that effect, problem, or death was not previously identified in nature, severity, or degree of incidence in the clinical investigational plan; or any other serious problem associated with a device that relates to the rights, safety, or welfare of subjects (21 CFR 812.3(s)). Any sight-threatening event, whether listed in the protocol or not, is considered to be reportable as a UADE

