### 10.3 REPORTING ADVERSE EVENTS AND UNANTICIPATED ADVERSE DEVICE EFFECTS

Identification, collection, and reporting of adverse event information is the responsibility of the principal investigator or designated investigator. The investigator records the date of the event, its severity, treatment (if any) and the assessed relationship of the event to the study device on the Adverse Event Case Report Form (AE CRF).

Any ocular-related **serious adverse event (SAE)** should be reported to the study sponsor within one working day of learning of the event. Non-ocular-related SAEs should be reported to the study sponsor within two working days of learning of the event. Record all applicable information in the source document, enter into the EDC system and email the AE CRF to [[contact]](mailto:[contact]).

Any **unanticipated adverse device effects (UADE)** must be reported to the following two entities:

1. The study sponsor – Within one working day of the investigator first learning of the event, record all applicable information in the source document, enter into the EDC system and e-mail the AE CRF to [[contact]](mailto:[contact]); and
2. The reviewing IRB – As soon as possible, but no later than 10 working days after the investigator first learns of the event, report per the IRB's instructions.

The sponsor will conduct an evaluation of unanticipated adverse device effects. If the sponsor determines that an unanticipated adverse device effect presents an unreasonable risk to subjects, parts of the investigation presenting risks will be terminated. Termination will occur no later than 5 working days after the sponsor makes such a determination and no later than 15 working days after the sponsor first received notice of the effect.

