### **12.6.2 PRIMARY SAFETY ENDPOINT**

The primary safety endpoint is the incidence of procedure (TearCare)/treatment (Restasis)-related adverse events.

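### The primary safety endpoint counts Restasis-related adverse events, but the text asks only for relationship to TearCare, and the by-group ocular event summaries set no time window or rule for control events after the Month 6 TearCare procedure

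*Combined protocol and SAP*

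**What the plan says.** **Endpoint.** Protocol 12.6.2: "The primary safety endpoint is the incidence of procedure (TearCare)/treatment (Restasis)-related adverse events". Section 6.2 lists the same endpoint and adds that "all adverse events will be recorded".

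**Recording.** Section 10 says that "the assessed relationship of the event to the study device will be recorded on the Adverse Event Form", and 10.3 repeats this for the case report form. Section 7.1 fixes what the device is: "TearCare procedures using the TearCare System (study device) will be compared with Restasis (control group". Section 10.1 defines an adverse event as "Any untoward medical occurrence in a subject who has been treated with the device", with or without a causal link. Under section 10, ocular events are documented whatever their cause. Non-ocular events are recorded only if they are serious or "are believed to be related to the study device or a study procedure". Section 10.2 refers sites to the Restasis label for potential events.

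**Analysis.** Sections 12.6.4 and 22.6 report events by group and summarise ocular events in two ways: the proportion of subjects with any event, and an incidence rate that counts repeats. Sections 12.2 and 22.1 define a safety population, analysed as treated, for all safety assessments. Section 12.6.1 tabulates all adverse events by visit and study group.

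**Follow-up.** Controls have one TearCare procedure at Month 6 (7.1). The schedules end at Month 24 for TearCare and Month 12 for controls (synopsis, Tables 3 and 4). SAP 22.4.1 counts subjects available at 24 months in each group.

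**The concern.** The endpoint needs two causality judgements, one for each treatment, and the text supplies only one. If sites follow it literally, the Restasis side of the endpoint has no stated causality record. A non-serious non-ocular event caused by TearCare is recorded, while one caused by Restasis may be dropped. That filter acts on one arm only.

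The second problem is in the by-group ocular summaries, which count events of any cause. The arms have different scheduled follow-up, and controls receive the test treatment halfway through theirs. Without a stated window, two distortions are possible, and they run in opposite directions. Longer follow-up can create an apparent TearCare excess, and events caused by TearCare can be counted against Restasis. Safety is half of the primary objective, so a reader will look at these tables.

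**Working it through.** **Part 1: reading the text (the documents give no event rates).**

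1. The endpoint requires relatedness to TearCare or to Restasis (6.2, 12.6.2).
2. The relationship to be recorded is to the study device (10, 10.3), which is TearCare (7.1). The only mention of Restasis in section 10 is the pointer to its label, which is not a causality record.
3. The definition in 10.1 covers subjects treated with the device. Table 4 schedules event assessments for controls from baseline, before they receive the device.
4. The non-ocular filter in section 10 conflicts with the statement in 6.2 that all events are recorded. Whether a study procedure includes Restasis is unclear: 9.6.3 says that "the subject should undergo the applicable procedures described in the sections below", and those sections include Restasis distribution (9.6.5).

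**Part 2: window and crossover.**

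The plan's own safety figure comes first. SAP 22.4.2 expects 98 TearCare subjects at 24 months with 10% dropout per 6 months: 150 × 0.9⁴ = 98.4. (The current minimum of 155 gives 101.7.) The margins 1.96·√(p(1−p)/98) at p = 5%, 10% and 20% are 4.3%, 5.9% and 7.9%, against 4.4%, 6.0% and 8.1% stated. Safety precision is therefore set at 24 months. The 6-month sentence in 12.5 stands under the effectiveness heading, so a 6-month safety window cannot be inferred from it.

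*Inputs for the illustration.* Dropout is 10% per 6 months (12.7, 22.4.2), with 11% also given in 12.7. Scheduled follow-up is 24 v 12 months, or k = 4 v 2 six-month periods. The event risk p per 6 months is assumed and equal in both arms. Hazards are constant: λe = −ln(1−p), λd = −ln(0.9) = 0.10536.

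(a) Any-event proportion, all scheduled follow-up pooled:
P(k) = λe/(λe+λd) × [1 − (0.9(1−p))^k]; ratio P(4)/P(2) = 1 + (0.9(1−p))².

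| assumed p | TearCare | Control | ratio |
|---|---|---|---|
| 2% | 6.4% | 3.6% | 1.78 |
| 5% | 15.2% | 8.8% | 1.73 |
| 10% | 28.5% | 17.2% | 1.66 |
| 20% | 49.7% | 32.7% | 1.52 |

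At p = 5% with 11% dropout, the ratio is 1 + (0.89 × 0.95)² = 1.71.

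(b) Person-time in 6-month units, (1 − 0.9^k)/λd: 0.949 (k = 1), 1.803 (k = 2), 3.264 (k = 4). The share of control person-time after the Month 6 procedure is (1.803 − 0.949)/1.803 = 47%. If controls were followed to Month 24, as 22.4.1 implies, the length artefact would disappear but the share would be (3.264 − 0.949)/3.264 = 71%. If the summaries stopped at Month 6, it would be zero.

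(c) Incidence rate. Counted per subject, exposure alone gives 3.264/1.803 = 1.81. Counted per person-time, the ratio is 1.0 at equal constant risk.

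(d) Assumed 5% risk per procedure and none from Restasis, analysed by randomised group. TearCare, with procedures at Day 0 and Month 5: 0.05 + 0.95 × 0.9^(5/6) × 0.05 = 9.4%. Control column: 0.9 × 0.05 = 4.5%, all from the crossover procedure.

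(e) A cut at the Month 6 visit, not a fixed day, leaves a small imbalance because the windows are 170–210 v 150–180 days. At the midpoints (190 v 165 days; 6 months taken as 182.5 days) and p = 5%, the result is 4.9% v 4.3%.

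**The case against.** On part 1, the adverse event form is not in the documents and may well ask about Restasis. The endpoint itself presupposes a relatedness judgement, ocular events are documented regardless of cause, and controls have event assessments throughout. A reader might infer that control-arm causality was never collected, or that controls cannot have an adverse event before Month 6. The documents support neither: the first depends on an unseen form, and Table 4 contradicts the second. What stands is that the written rules do not name Restasis and that 6.2 and section 10 disagree.

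On part 2, a reader might infer that the summaries have no denominator and no crossover rule at all. That goes too far. The safety population is a denominator for the proportion, and analysis as treated is a rule. The rule is incomplete: it does not say how a subject who received both treatments is split, and 12.6.4 speaks of study group where 22.6 speaks of treatment group.

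It is also tempting to conclude that TearCare-caused events will be charged to Restasis. Result (d) holds only for analysis by randomised group; an as-treated reading could place those events under TearCare. Nor does section 9.3 contradict the schedules. Its 24 months is an upper limit, which a 12-month control schedule satisfies; only 22.4.1 clearly conflicts. The by-visit tables in 12.6.1 partly separate the periods, but they do not define the two ocular summaries.

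**Conclusion.** The point holds and should be fixed, with medium confidence.

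- **Attribution.** The text leaves the Restasis side of the primary safety endpoint without a stated causality record and may drop some non-serious non-ocular events in one arm only. The size cannot be calculated, and a Restasis field on the form would remove most of this part.
- **Window.** The ocular proportion and rate have no window, the rate has no person-time basis, and control events after Month 6 have no clear home. If all scheduled follow-up is pooled, equal risk could appear as a ratio of about 1.5 to 1.8 in the proportion, for assumed risks of 20% down to 2% per 6 months. These figures illustrate the gap; they do not correct a stated number. They rest on assumed event rates, constant hazards and the plan's dropout.

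The comparison is descriptive. No hypothesis test, power figure or success rule is affected.

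**What to change.** 1. In sections 10 and 10.3, record relationship separately to the TearCare device or procedure and to Restasis. Query control-arm events already entered.
2. In 10.1, extend the definition to subjects treated with either product.
3. Reconcile 6.2 with section 10 so that non-ocular events related to either treatment are recorded.
4. In 12.6.4 and 22.6, define the between-group summaries over the randomised pre-crossover period with a common day cutoff. Report post-crossover control events and later TearCare events in separate columns, use person-time for the rate, and state how analysis as treated applies after Month 6.
5. Reconcile 22.4.1 with the control visit schedule.

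The cost is a text revision with IRB review as necessary (section 15) and possibly one form field. Retrospective causality assessment is weaker than prompt assessment, and non-ocular events that were never recorded may not be recoverable; the report should say so. Item 4 needs no new data, because event dates are already recorded.
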